b. Persistence to clozapine: Incident episodes of clozapine prescriptions will be identified by a 90 day look back period to identify a new episode of care. Persistence will be measured as the duration of the clozapine episode (in days) from the date of the first prescription record until the first gap of more than 45 days between prescriptions. Prescribing gaps will be calculated by first adding the days' supply to the dispensing date of each prescription to identify the date the prescription should be exhausted. Days that the patient is hospitalized will not be included in the calculation of episode duration. The first gap in prescribing of 46 days or more will be considered a discontinuation of the medication. An episode will only be right censored at the study endpoint, otherwise an episode can continue into the next time period. If a person has more than 1 episode of clozapine use during any time period, we will select the first episode.

Specific Aim 2: We will measure two educational outcomes: self-reported competence of prescribers/clinical team in using clozapine and knowledge associated with clozapine treatment. These will both be measured before and after the 12-month intervention period. These outcomes have been selected, because they are measurable and pilot data has already established that prescribers/clinical team will rate competence and answer questions on clozapine knowledge. In addition, we will pilot-test all questions and review the self-reported competence measure prior to the administration of the CHAMPION intervention.

a. Competence: Our measurement of competence will be based upon self-report assessment guided by Bandura's theory of self-efficacy (2, 3) and we are using a definition of competence as "the perceived self-efficacy rating of one's judgment to use clozapine"(2, 4). We will use a Visual Analog Scale (VAS) (0-100 mm) will serve as the primary outcome. Self-reported competence ratings will be evaluated for the overall use of clozapine and for each of the CHAMPION session topic areas. The VAS format has been found to be superior

CHAMPION PROTOCOL

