to using a standard Likert scale for self-reported competence evaluation (2). Self-efficacy ratings of competence have been shown to be increased in a mental health ECHO model (6); are recommended as a measure for approaching measurement of practice outcomes (7); and, when using VAS to measure self-efficacy competence, have been found to be a reliable and valid measure for this construct (8-10).

b. Knowledge: We will use multiple-choice questions (MCQ) to assess knowledge. The knowledge-based test questions will consist of 52 questions that will cover 2 questions per 26 topic areas and will conform to best practices and guidelines for design of the questions (11). MCQ have been used to assess knowledge with ECHO models (6, 12) and are known to be a reliable and valid measure for measuring knowledge (11). The total score will range from 0-52 correct answers.

Power

Hypothesis 1: Considering the intent to treat (ITT) approach to analyses, we will be able to assess administrative data prescription records for all prescriber participants regardless of their level of participation in the CHAMPION intervention sessions or other research data collections efforts. Missing data will be a concern only for those time periods where prescriber participants were not practicing in the Maryland public health system (before or after the intervention time period). We assume that we will have administrative data records from at least 85% of the prescribers/clinical team across all time points. We calculated the needed sample size using PASS version 13 (13) for independent proportions in a clustered-randomized design with the following specifications: alpha-level = .05, power = .80, effect size (h) = .39 (small to medium) and ICC = .01 (prescribers/clinical team nested within site). Effect size is based on estimating an 11% improvement in the rate of clozapine prescribing in CHAMPION; e.g. a 4% rate of clozapine prescribing in the ETAU group and a 15% rate in the CHAMPION condition. The required sample size is 254 based on clusters of 4-5 prescribers/clinical team per site.

Hypothesis 2: Even with a conservative estimate of the number of patients per prescriber on clozapine, a high ICC (.20) for patients nested within prescriber, and a small effect (d = .3), the power to detect differences in clozapine persistence between conditions is greater than 95%.

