Hypothesis 3: Although the variables for hypothesis 3 are normally distributed, the specifications are the same and the power calculations are identical to those noted above. Based on literature described in Approach section 10 above, we anticipate changes in knowledge and competence to be large ($>.8$).

Hypothesis 4: Using the values above and the SAS macro from O'Rourke and MacKinnon (14), the power to detect indirect effects (mediation) will be greater than .80 when using the bias corrected bootstrap procedure when paths a and b are at least 0.3 (small to medium effects anticipated).

Statistical Analyses Overview

All data will be screened for errors using frequency and contingency tables and univariate and bivariate plots before formal analysis. These informal plots and summaries will allow us to be cognizant of data distribution characteristics before building regression models. We anticipate that our dependent variables will either have a distribution that is relatively bell-shaped or can be transformed to be relatively bell-shaped. Site will be included in all models as a random effect. Prescriber is nested within intervention arm, by design, and will be specified as a random effect in all analyses that include patient level data. The intercept will be designated as random to account for the non-independence across time point when appropriate. SAS PROC MIXED or GLIMIX will be used for the analyses described below (15).

CHAMPION PROTOCOL

Missing Data

All analyses will be conducted within an ITT framework. As described above, missing data for hypotheses 1 and 2 will be limited due to the use of Medicaid prescription records for those outcomes. For hypotheses 3 and 4, we will compare the baseline characteristics of the prescribers/clinical team who drop out prior to completing the 12-month assessment to those prescribers/clinical team who do complete the assessment. If necessary, we will investigate how estimates/results change over a range of several plausible assumptions regarding the missing mechanism together with multiple imputations to most accurately capture existent random variability.

Multiple Comparisons

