To control for Type I errors, we will use the sequential Bonferroni-type procedure for dependent hypothesis tests of Benjamini and Hochberg (16) to control the false discovery rate at 5%. The false discovery rate is the expected (or on average) proportion of falsely rejected hypotheses. This procedure will be applied to the family of tests on the multiple associated measures corresponding to each aim. We will also control for if randomized to site or individual.

Analyses for Each Specific Aim and Hypothesis

Specific Aim 1: To determine the effect of 12 months of exposure to CHAMPION on the clozapine prescribing practices of prescriber participants and the objectively measured medication persistence of the patients prescribed clozapine.

Specific Aim 1, Hypothesis 1: *Relative to the prescribers/clinical team randomized to the ETAU condition (POC and consultation), prescribers/clinical team randomized to CHAMPION will significantly increase the proportion of patients in their care who are prescribed clozapine, as assessed using Maryland Medicaid prescription data.* Clozapine prescribing will be measured as the proportion of patients with any clozapine prescriptions (See Approach 5a). We will use a mixed-effects, 2-level model generalized linear mixed model (SAS Proc GLIMIX, log link) with percent adherence as the dependent variable and treatment group (CHAMPION/ETAU), time (pre-CHAMPION year (t=1), CHAMPION year (t=2), follow-up CHAMPION year (t=3), and time by treatment group as the independent variables of interest. However, since the main outcome will be calculated at t=3, a contrast statement, within the context of the full model, will be used to compare the two treatment conditions at t = 3, controlling for baseline, to test the primary hypothesis with a random site effect to account for intra-site correlation (ICC). The test of hypothesis 1 will operationally be the test of whether the coefficient of the CHAMPION/ETAU condition term is significantly >0 (two-sided test) at time t = 3. Post hoc analyses will use the same model to test effects at t = 2.

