Specific Aim 1, Hypothesis 2: *For patients who are prescribed clozapine, the patients of prescribers/clinical team randomized to CHAMPION will exhibit significantly greater persistence to clozapine treatment compared to patients of prescribers/clinical team randomized to the ETAU condition, as assessed using Maryland Medicaid prescription data.* Persistence (Approach Section 5b) will be measured as number of days of clozapine use. An episode will be identified as having begun during the 1 year prior to CHAMPION, during CHAMPION, or in the year after CHAMPION ends. A person can only have one episode in each of the time periods. We will use a generalized linear mixed-effects, 3-level model (SAS Proc GLIMIX, Poisson link), with a random site and a random prescriber effect to account for within site and within prescriber correlation (ICC). The longitudinal portion of the model will be treated as described for hypothesis 1. The test of hypothesis 2 will

CHAMPION PROTOCOL

operationally be the test of whether the coefficient of the CHAMPION/ETAU condition term is significantly greater than zero (two-sided test) at time 3. Post hoc analyses will use the same model to test for effects at time 2.

Specific Aim 2: To determine the effect of 12 months of exposure to the CHAMPION intervention on the knowledge and self-reported competence of prescribers/clinical team prescribing clozapine and how those mechanisms of change are associated with increased clozapine prescribing and persistence.

Specific Aim 2, Hypothesis 3: *Relative to the prescribers/clinical team randomized to the ETAU condition, prescribers/clinical team randomized to CHAMPION will demonstrate significantly increased levels of knowledge (correct number of MCQs) and self-reported competence (mean score on 0-100 mm VAS).*

Knowledge and competence are continuous measures that can be assumed to be normally distributed.

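### Hypothesis 2 models days on clozapine as Poisson with no allowance for overdispersion: error is moderately inflated if the arms are compared at t=3, and severely inflated if the test is change from baseline

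*Combined protocol and SAP*

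**What the plan says.** Persistence is the length of a new clozapine episode. Under Specific Aim 1, Hypothesis 2 it "will be measured as number of days of clozapine use", and a patient contributes at most one episode per period.

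The model is stated in one sentence: "We will use a generalized linear mixed-effects, 3-level model (SAS Proc GLIMIX, Poisson link), with a random site and a random prescriber effect". For the time structure the plan refers back: "The longitudinal portion of the model will be treated as described for hypothesis 1". Under Hypothesis 1 that structure is arm, three periods and their interaction, with a contrast that "will be used to compare the two treatment conditions at t = 3, controlling for baseline". The Hypothesis 2 test itself is then said to "operationally be the test of whether the coefficient of the CHAMPION/ETAU condition term is significantly greater than zero (two-sided test) at time 3".

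Statistical Analyses Overview adds one general line: "The intercept will be designated as random to account for the non-independence across time point when appropriate". It does not name the unit that carries this intercept. Neither that section nor the Hypothesis 2 text mentions overdispersion, an estimated scale, a negative binomial form or empirical standard errors.

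**The concern.** After the random effects, a Poisson model leaves no room for spread beyond the mean. Site and prescriber intercepts describe how sites and prescribers differ on average. They do not describe how two patients of one prescriber differ, or how one prescriber's baseline episodes differ from that prescriber's follow-up episodes. For durations in days this leftover variation is large, and the model treats it as nearly absent. The fault is separate from censoring and remains when every episode is seen to its end.

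At stake is the validity of one of the two Aim 1 hypotheses. There is a smaller knock-on under Multiple Comparisons. If Hypotheses 1 and 2 form the Aim 1 family, a spuriously small Hypothesis 2 p-value moves the Benjamini-Hochberg threshold for Hypothesis 1 from 0.025 to 0.05.

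**Working it through.** **1. The plan's own power figure.** The Power section claims more than 95% for Hypothesis 2 with d = 0.3 and ICC = 0.20, without giving patients per prescriber (m). Alpha is taken from Hypothesis 1 ("alpha-level = .05, power = .80"), two-sided. Effective n per arm = N·m / (1 + (m−1)·0.20) / 2, and power = Φ(0.3·√(n/2) − 1.96).

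- N = 300: m = 2 gives n = 250 and power 0.918; m = 3 gives n = 321 and power 0.967.
- N = 255 (85% of 300): m = 3 gives 0.939; m = 4 gives 0.966.

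So the claim is attainable with 3 to 4 patients per prescriber, but for a normal outcome, not for the Poisson model.

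**2. The power inputs conflict with the Poisson variance.** ICC = 0.20 puts 80% of the variance between patients of the same prescriber. Assume a mean of 200 days and CV 1 (variance 40,000). The within-prescriber variance is then 0.8 × 40,000 = 32,000, where Poisson allows 200: √160 = 12.6. At CV 0.5 it is √(8,000/200) = 6.3. Conversely, if Poisson held with ICC 0.20, the total variance would be 200/0.8 = 250, the SD about 16 days, and d = 0.3 about 5 days.

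**3. Simple theory for a within-prescriber contrast.** The standard error is too small by k = √(mean × CV²), and the false-positive rate is 2Φ(−1.96/k).

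| Mean (days) | CV | k | False positives |
|---|---|---|---|
| 100 | 0.7 | 7.0 | 78% |
| 200 | 0.7 | 9.9 | 84% |
| 100 | 1 | 10.0 | 85% |
| 200 | 1 | 14.1 | 89% |

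**4. Simulation under no effect.** Inputs from the protocol: 60 sites of 5 prescribers, three periods, site and prescriber intercepts. Assumed: scale fixed at 1, episode lengths and volumes, no censoring. A prescriber log-variance of 0.288 with exponential durations gives ICC = (e^0.288 − 1)/(2e^0.288 − 1) = 0.20. There were 150 runs per row, of which 30 were also fitted with a constrained baseline. Cells show the SE ratio (empirical SD / mean model SE) and the false-positive rate.

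| Mean days | Episodes per prescriber-period | Log-variance, prescriber / site | Shape | Arm difference at t=3 | Change t=1 to t=3 | Constrained baseline |
|---|---|---|---|---|---|---|
| 180 | 3 | 0.288 / 0 | exponential | 1.34, 13% | 16.5, 91% | 15.5, 90% |
| 180 | 3 | 0 / 0 | exponential | 1.71, 23% | 13.0, 91% | 12.5, 97% |
| 180 | 1 | 0.288 / 0 | exponential | 1.51, 20% | 15.4, 90% | 13.9, 83% |
| 180 | 10 | 0.288 / 0.02 | exponential | 1.17, 9% | 16.4, 92% | 12.8, 93% |
| 100 | 3 | 0.05 / 0 | exponential | 1.55, 20% | 10.1, 89% | 9.5, 93% |
| 300 | 3 | 0.288 / 0 | exponential | 1.34, 13% | 21.3, 93% | 20.0, 93% |
| 180 | 3 | 0.288 / 0 | Weibull 1.5 | 1.18, 12% | 11.1, 89% | 9.5, 90% |

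A second set used a prescriber intercept only (254 prescribers; 0.5, 1 or 3 episodes per period; mean 100 or 200 days; CV 0.7 or 1; 300 runs each). It gave 84-90% for change and 16-29% for the t=3 coefficient.

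The two contrasts differ because the estimated prescriber variance absorbs much of the patient-level spread when prescribers are compared between arms. It cancels out of a change within prescribers.

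**5. End-of-study censoring.** Take entry as uniform over the final 365 days, follow-up stopping at the end of that year, and latent means of 100 to 300 days (exponential or Weibull 1.5). Root variance/mean of the observed t=3 durations is then 6.4 to 8.5. False-positive rates were not simulated with censoring.

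**6. Same model with dispersion freed** (mean 180, 3 episodes, ICC about 0.20, 80 runs). An estimated residual scale gave SE ratio 0.98 and 4% for the t=3 difference, and 1.10 and 9% (Monte Carlo error about 3 points) for change. A prescriber-clustered sandwich SE gave 5.5-6.4% in 1,500 simulations.

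**The case against.** A reader might infer that standard errors are 10 to 15 times too small whatever is tested, and that a false finding of better persistence under CHAMPION is nearly certain. The documents do not support that, for four reasons.

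- **Contrast.** The Hypothesis 2 text words the test as the condition coefficient at time 3. On that wording the inflation is moderate. The severe figures need the baseline control imported from Hypothesis 1 to mean change or a constrained baseline. That reading is natural, since baseline is one of the modelled outcomes, but the plan does not say how baseline enters.
- **Episode lengths.** The documents give no mean, spread or volume. The multiplier moves with these assumptions, and end-of-study censoring lowers it at t=3.
- **Direction.** The test is two-sided. With no true effect about half of false rejections would favour ETAU, so even on the severe reading a false result for CHAMPION occurs in about 42-48% of trials (half of 83-97%).
- **Other provisions.** The overview allows a further random intercept. If placed on the patient it could absorb part of the extra variation; this was not simulated. It names no unit, is conditional, and is not a rule for overdispersion. The planned plots and transformations are not one either.

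The plan also ties its primary hypothesis to Hypothesis 1, although persistence is listed under Primary Outcomes. The spill-over to Hypothesis 1 is small.

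What stands after all this is that the variance model is wrong for days and nothing stated corrects it.

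**Conclusion.** The concern holds, with a size that depends on which contrast is meant. As written, the Hypothesis 2 standard errors are too small, and neither reading keeps the two-sided 5% level in any scenario simulated.

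- Change from t=1, or a constrained baseline: roughly 7 to 20 times too small for uncensored episodes, with simulated false positives of about 83-97%. With end-of-study censoring, root variance/mean at t=3 is about 6 to 9.
- Plain arm coefficient at t=3: about 1.2 to 1.7 times too small, false positives about 9-29%.

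That the Poisson variance is inadequate follows from the plan's own ICC together with any plausible spread of durations. The exact multipliers rest on assumed mean lengths of 100 to 300 days and assumed numbers of episodes. The error could fall in favour of either arm.

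**What to change.** In Specific Aim 1, Hypothesis 2:

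1. Name the exact contrast and state how baseline enters: change from t=1, constrained baseline, or arm difference at t=3.
2. Replace the fixed Poisson variance with one of these:
   - the log-mean model with cluster-robust (empirical) standard errors at the level of randomisation: site, or the individual prescriber where randomised individually;
   - a free-dispersion model (estimated scale, negative binomial, or gamma with log link) with a prescriber-by-period random effect.
3. If Hypothesis 2 moves to a time-to-discontinuation model, carry the same clustering over.
4. State which unit carries the optional random intercept in Statistical Analyses Overview.

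The simulated remedies were prescriber-level clustering and an estimated scale. Site-level clustering was not simulated, so its performance with the actual number of sites should be checked.

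The cost is SAP wording and a few lines of code. Confidence intervals for Hypothesis 2 will be wider, and the stated power above 95% should be rechecked under the corrected model with the number of patients per prescriber written down.

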Sites included in the CHAMPION will receive the POC ANC device to use during the 12-month study (and for 12 months post intervention) as well as access to clozapine consultation as described in the ETAU condition for 12 months during the intervention and 12 months follow-up. In addition, approximately half of the CHAMPION sites/individuals will receive biweekly ECHO telementoring education sessions. These telementoring sessions will occur simultaneously for all intervention sites and may consist of one or two identical sessions during the week. Each session will consist of a 15-20-minute didactic period on specific topics which will be followed by approximately 1 hour of site supplied case and patient consultations. All the prescribers and the clinicians at the sites are welcome to attend the online session even if they enroll for study inclusion or not. Attendance will be tracked by the study team at the beginning of each session.

The session will conclude with a discussion and question and answer period. At the end of the session the team of clozapine experts will provide a written summary of treatment recommendations regarding the cases. Each CHAMPION session will have at least one clozapine expert delivering the didactic topic and at least 2 additional clozapine experts providing mentoring for the case-based consultation session. This will allow us to call upon the diverse group of experts in our proposed study personnel. We will complement the sessions with dissemination of any relevant publications, toolkits and tips.

Enhanced Treatment as Usual (ETAU) Condition and Justification

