Analysis of Secondary and Exploratory aims.														
Archive ECHO lectures for website at end of 12 months														
Period of Medicaid Data Collection 2 (Aim 1)														
Post Testing on Knowledge and Self-Reported Competence (Aim 2)														
Meetings with NASHMPD														
Analysis of Project ECHO Post data														
Make videotaped ECHOs available to all participants once 12-month Medicaid data completed.														
National Webinar with NASHMPD and APA CSS SMI														
Submit symposium abstract to national														

CHAMPION PROTOCOL

meetings, e.g. IPS, SIRS														
Data Repository Submission														

STATISTICAL DESIGN AND POWER

Primary Outcomes

Specific Aim 1: The primary outcome examines Maryland Medicaid (and HMIS for inpatient) prescription data, which will be used to assess the increase in the proportion of patients treated with clozapine for those in the care of prescribers/clinical team randomized to the CHAMPION relative to the ETAU condition. We will also examine persistence in the use of clozapine for patients who are prescribed clozapine under the care of prescribers/clinical team randomized to CHAMPION compared to prescribers/clinical team randomized to the ETAU. The specific outcome assessments using Medicaid data include:

a. Proportion of clozapine prescriptions: Clozapine prescribing rates will be calculated from Medicaid prescription data. National Prescriber Identification (NPI) numbers will be used to identify the antipsychotic prescription records for each prescriber in the study. The denominator will be the number of unique individuals with a diagnosis of schizophrenia who had at least 1 prescription for an antipsychotic during each time period (12 months prior to start of study, during active study participation, and 12 months after the intervention period ends). For each individual in the sample, an indicator will be created that reflects whether the person had any prescription for clozapine during each of the time periods.

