Transformations will be used if necessary. They will be measured at two time points (baseline and end of the 1-year CHAMPION). A General Linear Mixed Model (Proc MIXED) will be used to estimate the effects of the two groups on change in knowledge and competence with site as a random effect. The test of hypothesis 3 will operationally be the test of whether the coefficient of the CHAMPION/ETAU condition term is significantly greater than zero (two-sided test) at the post CHAMPION time point controlling for baseline. In exploratory analyses, we will examine individual competence scores related to outcomes as above while controlling for multiple comparisons.

Specific Aim 2, Hypothesis 4: *Prescriber self-reported competence will mediate the effect of the CHAMPION on clozapine prescribing and persistence.* A separate model will be used for each outcome. The independent variable will be group assignment, the dependent variable will be rate of clozapine prescribing during the year following CHAMPION and the persistence of clozapine episodes, and the mediator will be the overall self-reported competence score (0-100 mm VAS) measured at 12 months, controlling for baseline. We will use the product of coefficients approach to test mediation. The rationale behind this method is that mediation depends on the extent to which the independent variable changes the mediator (i.e., path a), and the extent to which the mediator affects the outcome variable (i.e., path b). The PROCESS (17) macro for SAS will be used to generate 95% bias corrected confidence intervals for the relative indirect effects and other parameters.

Exploratory Analyses

We will examine the role of race in moderating the effects of CHAMPION. To determine whether there was differential benefit of the program for the AA patients, race and interaction terms (time by race) will be added to the models described above. Despite our previous work, it is possible that increases in prescribing will not occur similarly between AA and Caucasian patients, however, we will use data collected to adapt future iterations of the topics related to AA if we do not see similar improvements in prescribing. Specifically, we will examine the two competence questions related to AA and ascertain the relationship of these specific measures to prescribing for AA and Caucasian patients. We will also look at other variables by site and patient that may contribute to outcomes and will analyze the other clinicians and examine.

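### Hypothesis 4 can count clozapine started before month 12 as mediated by competence that is first re-rated at month 12

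*Combined protocol and SAP*

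**What the plan says.** Under Specific Aim 2, Hypothesis 4, "the mediator will be the overall self-reported competence score (0-100 mm VAS) measured at 12 months, controlling for baseline". Competence is rated only twice, before the intervention and at the end of the CHAMPION year. The outcomes are stated as follows: "the dependent variable will be rate of clozapine prescribing during the year following CHAMPION and the persistence of clozapine episodes". The test is the product of path a (arm to mediator) and path b (mediator to outcome), with bias-corrected intervals.

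The prescribing rate is defined under Primary Outcomes, item a. For each patient, "an indicator will be created that reflects whether the person had any prescription for clozapine during each of the time periods". This is any use in the period, not new use.

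For persistence, Primary Outcomes item b says: "Incident episodes of clozapine prescriptions will be identified by a 90 day look back period to identify a new episode of care". It adds: "An episode will only be right censored at the study endpoint, otherwise an episode can continue into the next time period". Specific Aim 1, Hypothesis 2 allows three start periods: "An episode will be identified as having begun during the 1 year prior to CHAMPION, during CHAMPION, or in the year after CHAMPION ends". Hypothesis 2 is then tested at time 3. Hypothesis 4 does not repeat that limit.

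Under CHAMPION Intervention Condition, each session has a short didactic part "followed by approximately 1 hour of site supplied case and patient consultations", and the experts then issue written recommendations on those cases.

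**The concern.** A mediator should come before the outcome that it is said to explain. Here the mediator is fixed at month 12, but a patient started in t=1 (the year before CHAMPION) or t=2 (the CHAMPION year) who fills once in t=3 (the follow-up year) counts as t=3 prescribing. Read literally, the persistence outcome admits episodes that began before month 12.

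The reverse direction is plausible in this trial. Case consultation could lead a prescriber to start patients in t=2 without first raising competence. Having started them, the prescriber may rate competence higher at month 12, and the same patients then carry over into the t=3 rate. The product of coefficients cannot tell this chain from the hypothesised one. The baseline adjustment is attached to the competence score, so no earlier prescribing is held constant.

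The Background names competence as the target mechanism, and the pilot evidence it gives is a correlation. Hypothesis 4 is a named hypothesis of Aim 2. What is at stake is how a significant indirect effect may be read.

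**Working it through.** **1. The plan's own figures.** These come from the Power section: alpha .05, power .80, h = .39, ICC .01, clusters of 4-5, data for 85% of prescribers.

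- n per arm = 2 × ((1.960 + 0.842)/0.39)² = 103.2, rounded up to 104, so 208 in total.
- Clusters of 5: 208 × (1 + 4 × 0.01)/0.85 = 254.5. Clusters of 4: 208 × 1.03/0.85 = 252.0. The stated 254 is reproduced.
- The plan states power above .80 for Hypothesis 4 with both paths at least 0.3. By simulation at N = 254 it is about .99 if both paths are standardised, and about .72 if path a is a between-arm standardised difference of 0.3. The plan does not say which scale it means. Neither figure bears on the direction of effect.

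**2. A trial in which competence has no effect on prescribing.**

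- From the documents: N = 254; t=3 rates of 4% and 15%; an arm effect of 0.8 on competence; bias-corrected bootstrap.
- Assumed: 20 patients per prescriber; 25-75% of t=3 clozapine patients started before month 12 (carry-over); competence rises by r (residual SD 0.85) for each SD of pre-month-12 starts, with r from 0 to 0.3. Site clustering was not modelled.

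**3. One cell by hand (50% carry-over, r = 0.2).**

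- Carried-over rates are 0.5 × 4% = 2% and 0.5 × 15% = 7.5%, a difference of 0.055.
- Within-arm variance of a prescriber's carried-over rate: 0.02 × 0.98/20 = 0.00098 and 0.075 × 0.925/20 = 0.00347, mean 0.00222.
- SD over all prescribers: √(0.00222 + 0.0275²) = 0.0546.
- Path a = 0.8 + 0.2 × 0.055/0.0546 = 1.00.
- Path b = covariance/variance within arm = (0.2 × 0.00222/0.0546) / (0.2² × 0.00222/0.0546² + 0.85²) = 0.00815/0.752 = 0.0108.
- a × b = 0.0108. Against the total effect of 0.15 - 0.04 = 0.11, that is about 10% of the effect, all of it spurious. Simulation of this cell also gave about 10%.

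**4. Share of trials declaring mediation when the true value is zero** (300-400 trials per cell; standard error about 1.3 points at 5% with 300 trials):

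| Carry-over | r = 0 | r = 0.1 | r = 0.2 | r = 0.3 |
|---|---|---|---|---|
| 25% | 6% | 16% | 43% | 68% |
| 50% | 7% | 27% | 63-65% | 91% |
| 75% | 4% | 30% | not run | about 98% |

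For r of 0.1 or more, between 3.5% and 20% of the effect is called mediated. With 10 or 40 patients per prescriber, the r = 0.2, 50% cell gives 71% or 58%. Separate runs expressed feedback as points on the 0-100 scale per patient started. They gave 4-9% with none, and 9-43%, 22-76% and 40-93% at 1, 2 and 3 points.

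**5. Candidate remedies (r = 0.2, 50% carry-over).**

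- Adding the t=1 rate to the any-use model does not help: 63-66%.
- Making new t=3 starts the outcome gives about 7-9%, provided prescribers have no lasting differences in propensity to prescribe.
- With such differences (gamma variance 0.5), any-use gives 81%, any-use plus the t=1 rate 76%, and new starts alone about 28%. New starts adjusted for both t=1 and CHAMPION-year prescribing give about 8%. The separate runs show the same pattern: up to 24% for new starts alone, and about 4-8% with both covariates.

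**The case against.** The strongest reply is that the bias depends on a quantity nobody has measured. The documents do not show that starting patients raises self-rated competence, and with r = 0 the planned test is close to nominal. This stands. A reader might infer that Hypothesis 4 will credit earlier prescribing to competence, or that Aim 2 will be answered wrongly. The documents support only that this can happen. Hypotheses 1, 2 and 3 are untouched, and Aim 2 itself is partly worded as a question of association.

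Second, the prescribing window does lie after month 12, and persistence may have been meant to follow the time-3 test of Hypothesis 2. On that reading, the 90-day look-back makes the episodes new or restarted ones, and the point largely falls away for persistence. A reader might infer that the plan definitely analyses episodes that ended before the mediator was rated. The text leaves this open; it does not settle it.

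Third, new starts are a different outcome. They leave out competence gained early in CHAMPION that led to t=2 starts, and competence that helps keep existing patients on treatment. Choosing patients not on clozapine at the end of t=2 also conditions on a status that the intervention is meant to change. This stands too. It is why new starts should sit beside the any-use outcome and not replace it. A reader might also infer that new starts alone, or the t=1 rate alone, cures the problem. Step 5 shows that neither does.

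**Conclusion.** The concern holds conditionally. On the text, the mediator is rated at month 12, the t=3 rate includes patients started earlier, persistence has no stated start date, and prior prescribing is not adjusted for. Nothing in Hypothesis 4 separates the two directions.

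The size cannot be known from the documents. With no feedback, false mediation stays at about 4-7%. With the assumed feedback (r = 0.1 to 0.3) and 25-75% carry-over, it runs from 16% to about 98%. These figures rest on assumed patients per prescriber, carry-over and feedback, and should be read as a range of possibility and not as a forecast. The change should be made before the mediation analysis is run. It does not affect the primary result.

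**What to change.** In Specific Aim 2, Hypothesis 4:

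1. Limit persistence to episodes that begin after the 12-month assessment, that is, the t=3 episodes. If this was already the intention, it is only a clarification.
2. Add the prescriber's t=1 clozapine rate as a covariate in both paths, beside baseline competence. State that this alone does not remove the carry-over problem.
3. Keep the any-use t=3 rate and report its mediation result as associational. Beside it, pre-specify an analysis of new t=3 starts (using the existing 90-day look-back) among patients not on clozapine at the end of t=2. Add a sensitivity analysis, labelled as such because the covariate arises after randomisation, that also adjusts for CHAMPION-year prescribing. Claim mediation of later prescribing only if the new-start analysis agrees.

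The cost is plan wording and reprogramming. The dispensing dates, medication start dates and prescriber identifiers needed are already among the listed data elements. There will be fewer events and wider intervals. The new-start analysis omits competence effects acting through t=2 starts or retention, and it conditions on a post-randomisation status; the report should say so.
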